## Procedures

Personnel training. Before subjects are enrolled in the study, a comprehensive study manual will be developed and distributed to all study personnel describing all study procedures. Under the supervision of the Principal Investigator, the Project Director will train the GRAs on all procedures. Training will include completion of the USF investigator/researcher educational program for human subject protections, Collaborative Investigator Training Initiative (CITI), developed by experts in the field of human subject's protections. The study staff will be trained on all aspects of data collection, using all the monitoring equipment, as well as the medical record. Training on the entire procedure will be conducted by the Project Director and GRAs have achieved 100% accuracy of all procedures and data collection processes including subject recruitment, obtaining consent consistent with applicable state and federal statutes, intervention procedures, saliva sample collection, and taking digital images. After training is complete, each GRA will perform return demonstrations on all study procedures with the Project Director satisfactorily completing all critical elements identified (100% accuracy) before conducting study procedures independently. Each GRA will also be tested every 3 months throughout the study period to ensure that all critical elements of the procedure are included. This testing will be done by direct observation of study personnel conducting study procedures by the Project Director and will include reliability testing for data collection processes. If any critical element is found to be omitted or inaccurate, retraining and return demonstrations will occur immediately until the omissions are corrected. If study procedures are in progress, the Project Director will supervise study procedures to ensure that all critical elements are present until retraining and revalidation of the GRA can occur. Once data collection begins, the Project Director will review all data for completeness and appropriate entries before the data are entered into the study database. At the beginning of the data entry process a minimum of 1 in every 10 participant records will be checked against the original medical record for data errors. Records for review will be randomly chosen by the data manager. As the study progresses, the frequency of monitoring will be based on the results of previous data review. If the error rate is unacceptable then the monitoring will increase until the error rate is acceptable (less than 5% of all data).

Non-patient participants. Approximately 10 non-patient participants will be invited to provide saliva samples to validate the GCF collection process. Approximately 5 non-patients will be invited to provide a video of their tooth surfaces before and after tooth brushing to validate the randomized digital image selection method for plaque analysis. Each non-patient participant will be consented to publish the analysis results of the GCF samples or tooth surface videos. Non-patient inclusion criteria: must be  $\geq 18$  years of age; have at least one tooth to obtain saliva sample for GCF analysis or tooth surface video; and understand English for informed consent to publish analysis results of GCF sample or tooth surface video. Non-patient exclusion criteria:  $<18$  years old or edentulous and cannot obtain saliva for GCF

analysis or video of tooth surfaces for plaque analysis. Non-patient recruitment procedure: the Project Director will verbally announce availability to participate along with the eligibility criteria to the study team members and to the faculty and staff members of the USF CON Biobehavioral Lab; the Project Director will confirm each volunteer is  $\geq 18$  years of age; has at least one tooth; and understands English; the Project Director will explain the consent form in detail and assess participants level of understanding by requesting a return explanation of the consent to publish the analysis results of the GCF sample or tooth surface videos.

Recruitment and enrollment. All patients admitted to the Intensive Care Units at TGH who are intubated will be assessed for possible inclusion in the study. The PI, co-investigators, Project Director or GRAs will make daily rounds to the adult ICUs and ask the charge nurse to identify any patients, by room number, that have been intubated within the last 36 hours. A HIPAA waiver for screening and recruitment is requested for this study to allow the study staff to review the medical records for screening and recruitment purposes. If a patient meets study criteria (age 18 or older, within 36 hours of initial intubation, have at least one tooth, and they or their legally authorized representative able to provide informed consent in English or Spanish) and has no exclusions (anticipation by the clinical provider of imminent patient death, or medical contraindication to tooth brushing), the potential subject will be approached for a discussion about willingness to participate. If the subject is unable to provide consent due to sedation or inability to communicate, the legally authorized representative (LAR) will be approached, the study will be reviewed and permission for the subject to participate will be obtained from the LAR; in these cases, we will attempt to obtain assent of the subject as well, and will make additional attempts to consent the subject directly as their condition improves. In our experience, potential subjects who are critically ill, especially during the first 36 hours of intubation, are always sedated to some degree, and their ability to communicate effectively is compromised by endotracheal intubation; for these reasons, permission for the subject's participation has generally been obtained from the LAR. However, there may be rare occurrences when potential subjects are adequately oriented and lucid to be able to provide informed consent. Therefore, we will use a 2 step procedure (developed by Fan et al) to determine the patient's ability to provide informed consent. Step 1 is objective evaluation with the Richmond Agitation-Sedation Scale (RASS) and the Confusion Assessment Method for Intensive Care Unit (CAM-ICU). Patients who score -1, 0, +1 on the RASS indicating drowsy, alert, or restless respectively and are not delirious (CAM-ICU = No) will move to Step 2. Step 2 is assessment for competency using the MacArthur Competence Assessment Tool for Clinical Research: MacCAT-CR. This is the most widely used tool, and is the only tool that evaluates all four capacity domains (understanding, appreciation, reasoning, expression of a choice). Evaluation of Step 1 requires approximately 2-3 minutes, Step 2 requires approximately 15 minutes. Fan et al. found in consent evaluations of 150 ICU patients that 89% were sedated/delirious, and unable to provide consent; our experience in previous research is similar. Therefore, we expect that few potential subjects will move to Step 2. The LAR will then be contacted for those who fail Step 1 or Step 2. Subject's willingness to continue participation will be assessed on an ongoing basis throughout the project. We will follow the USF and TGH IRB Written Policies and Procedures, as well as the Florida regulations regarding appropriate use and definition of the LAR. The subject and the subject's LAR will be provided with an oral explanation of the nature of the study and study information, and information in writing, prior to seeking consent signatures. The information will include all elements required for informed consent, and will include all pertinent contact information as well as information about withdrawal from the study. Written documentation of consent will be obtained from the subject, if capable, or the LAR. If the potential subject or LAR does not wish to participate in the study, no additional interactions with the potential subject will take place. Further, subject's willingness to continue participation will be assessed on an ongoing basis throughout the project.

Once the subject has been enrolled, the Project Director will assign the subject to one of the three groups using a randomization schedule generated by [name]. A set of sequenced, sealed opaque envelopes will be prepared, each containing the assignment of an individual subject. At the time of enrollment, the Project Director will open the next envelope and proceed accordingly. [name] and the Data Manager will each keep a master copy of the randomization assignment.

Intervention and data collection procedures. Following obtainment of informed consent from the subject or LAR, subjects will be randomly assigned within 36 hours of intubation to one of three intervention groups which differ in frequency of tooth brushing (once, twice, or three times daily). The intervention, a standardized tooth brushing protocol developed and tested in the previous project, will be delivered by study personnel for 7 days, or until the subject is extubated if extubation occurs within the first 7 days.

Daily saliva periopaper GCF samples will be collected and digital images of teeth will be taken and identified only by the subject's arbitrary study number, not by any identifiable private information. GCF samples will be frozen at  $-70$  degrees in the Tampa General Hospital Office of Clinical Research Laboratory, and later transported to the

Biobehavioral Laboratory at the USF CON, and stored securely in the locked, limited access laboratory. Digital images of teeth will be obtained at close range such that photos will not include subject facial features.

Data will be obtained from the patient's medical record, from assessment of the subject's mouth, and from biologic fluids (gingival crevicular fluid, GCF, collected on filter paper). On study admission, the following data will be collected: demographic data (age, gender, smoking status, reason for admission), severity of illness data (APACHE information), and a count of decayed, missing and filled teeth (DMFT). The following data will be collected every day through the first seven days of mechanical ventilation, or until extubated if extubation occurs within the first seven days: digital photos of all teeth (for use in UM-OHI dental plaque assessment), a sample of GCF collected on Periopaper (for GCF IL-1 $\beta$  assay), Systemic Inflammatory Response Syndrome criteria from the medical record, positive epidemiologic surveillance reports for enrolled subjects for VAE (including VAP), bacteremia, and sepsis from the TGH Epidemiology Department records. For subjects who are extubated during the first 7 days of mechanical ventilation, the same data collected during the study intervention period will also be collected after extubation on days 1,3,5 after extubation. Data regarding length of intubation, length of ICU stay and length of hospital stay will also be calculated from the medical record.

All data, including digital photos, will be collected on laptops in the clinical setting; these laptops will remain in the possession of study personnel at all times (unless locked in a cabinet in the locked research office), and all study-related files will be password protected. At the conclusion of each subject's participation, that subject's data will be transferred from the laptop computer to a secure, password protected file on the USF Health server, under the direct supervision of [name], with access limited to study personnel. Study information obtained will be kept strictly confidential, and it will not be possible to identify any participant from the reports that may result from this research.

## **X. PLAN FOR CONTROL OF INVESTIGATIONAL DRUGS, DEVICES, AND BIOLOGICS**

N/A

## **XI. DATA ANALYSIS PLAN**

The data analysis approach for this trial is considered innovative in that it will focus on providing appropriate clinical practice guidelines through testing of non-inferiority and quantification of number needed to harm, as opposed to conventional testing of superiority among respective randomly-assigned treatment regimens. Specifically, we will first evaluate whether the single tooth brushing regimen is clinically equivalent (non-inferior) to brushing two or 3 times daily, and also quantify the respective risk versus clinical benefit of brushing multiple times daily. The sample size and power analyses (see below) are based principally on specific aim #1 and a one-sided test of non-inferiority for the once daily tooth brushing regimen.

Specific Aim 1 is to evaluate the clinical equivalence (non-inferiority) of three tooth brushing frequencies on oral health (dental plaque and mucosal inflammation) in critically ill adults receiving mechanical ventilation. To evaluate non-inferiority, we will use data from subjects who have at least 2 days duration of mechanical ventilation and at least 2 days of their randomly assigned tooth brushing regimen. Recognizing variable length of hospital stay and intubation, we will determine as the primary outcome the maximum difference in dental plaque since baseline assessment at the time of intubation. Whereas we would expect balanced distribution of the specific post-admission day in which this maximum difference is achieved between the 3 treatment arms (e.g. day 4, day 5, etc.), timing of the assessment will be included as a covariate along with baseline dental plaque score. Analysis of covariance (ANCOVA) will be used to compare adjusted dental plaque scores between the 1 and 3 times daily tooth brushing regimens. The test for non-inferiority of the single daily brushing regimen will be based on the 95% confidence interval for the adjusted difference between the 2 groups. For this analysis, we define non-inferiority as a modest between-group effect size of 0.50 or less (i.e. modest to low treatment effect associated with tooth brushing 3 times daily). Thus, if the upper limit of the confidence interval for the effect size is <0.50, then the single daily brushing regimen will be considered non-inferior to the 3 times daily tooth brushing regimen. If the non-inferiority test is not supported, a secondary test of the 1 versus 2 times daily brushing regimens will be conducted. Using this strategy, a direct test of non-inferiority of 2 versus 3 times daily is not required (see Table 2).

Specific Aim 2 is to quantify and compare the safety of three tooth brushing frequencies on serious adverse outcomes, including ventilator associated complications and clinically relevant healthcare-associated infections. For aim #2, a composite HAI endpoint will be constructed consisting of VAP, bacteremia, and sepsis. Since HAIs are anticipated to be rare events across the 3 tooth brushing regimens, no formal between-group statistical testing will be conducted. Instead, 95% confidence intervals will be calculated for the proportion of subjects with HAI in each treatment arm. In addition, using person days of observation (i.e. days since intubation), we will calculate incidence rates (IR) of HAI by treatment arm and then calculate the number needed to harm (NNH) using the single daily brushing regimen as the

reference group and the formulas:  $NNH_{21} = (1 / (IR_2 - IR_1))$  and  $NNH_{31} = (1 / (IR_3 - IR_1))$  where  $IR_n$  = observed incidence rate in each treatment arm. In the event that the formal test of non-inferiority fails for the single daily brushing regimen, we will define clinically-relevant “compromised” safety as an NNH of 100 per less. This would be interpreted as 100 individuals or less being treated with the multiple daily tooth brushing to develop an HAI that otherwise would not have occurred with the single daily brushing regimen.

Clinical recommendations defined *a priori* and developed from the analyses conducted for aims 1 and 2 will be developed as defined in Table 2.

Table 2. Application of study findings to tooth brushing frequency recommendations

Comparison Groups a	Non-Inferiority	NNH	Recommendation	Rationale
1 versus 3	Supported	N/A	1 time/day	1 time/day non-inferior and safe
1 versus 3	Not supported	$\geq 100$	3 times/day	1 time/day inferior, 3 times/day safe
1 versus 3	Not supported	$< 50$	1 time/day	1 time/day inferior, but 3 times/day safety concern
1 versus 3	Not supported	50 to 100	See 1 vs. 2	1 time/day inferior, but 3 times/day safety concern
1 versus 2 b	Supported	N/A	1 time/day	1 time/day non-inferior and safe
1 versus 2 b	Not supported	$\geq 100$	2 times/day	1 time/day inferior, 2 times/day safe
1 versus 2 b	Not supported	$< 100$	1 times/day	1 time/day inferior, but 2 times/day safety concern

aTimes per day of tooth brushing. bConducted if the 1 versus 3 test of non-inferiority is not supported and  $NNH_{31}$  is between 50 to 100. NNH: number needed to harm.

Specific Aim 3, to investigate patient factors that influence tooth brushing frequency benefit and risk in critically ill adults, is considered exploratory. Repeated measures linear mixed models will be fit treating dental plaque and mucosal inflammation as separate outcome variables (transformed if required), random group assignment as a 3-level ordinal predictor variable, and a range of possible patient-level predictors. Initially, bivariate correlations for potential continuous predictors and analysis of variance (ANOVA) for potential categorical predictors will be conducted to identify potential patient factors independently associated with dental plaque and mucosal inflammation. Interaction terms between tooth brushing frequency (scored 1, 2, or 3) and individual patient factors will be constructed to assess potential effect modification. The mixed models will be fit using the normal distribution, identity link, and specifying an autoregressive correlation structure. For assessment of safety, and assuming a sufficient number of HAs for model conversion, generalized estimating equations will be fit in the same manner as the linear mixed models while specifying the binomial distribution, log link, and an autoregressive correlation structure. Through these analyses, we aim to gain insight as to specific patient factors (e.g. presenting oral health) that may modify the clinical effectiveness and safety profile associated with frequency of tooth brushing.

**Statistical Power and Sample Size Justification.** As described above, our primary aim is to evaluate whether a single daily tooth brushing regimen is clinically non-inferior (defined as an effect size of  $\leq 0.50$ ) to a regimen of brushing twice or 3 times daily. The test is considered one-sided as there is no known or postulated biological mechanism to expect a better clinical result (lower plaque score) with the once daily brushing regimen, while at the same time, no reason to expect a higher risk of serious adverse events with this regimen as compared to 3 times daily brushing. To be conservative, we assume that up to 40% of subjects enrolled will have missing data or not provide analyzable data due to intubation for less than 48 hours or less than 2 days follow-up measurement of dental plaque and mucosal inflammation after intubation; this is consistent with our previous and current projects. The non-inferiority trial is powered based on conventional guidelines of type I error rate ( $\alpha$ ) of 0.10 and 95% desired power, and specifying a 1-tailed tolerance limit for non-inferiority as an effect size of 0.50. With these conditions, a sample size of 69 subjects per group (i.e. testing group 1 versus 3) is required. This group size will also be sufficient if the non-inferiority test is not supported, and a secondary test of the 1 versus 2 times daily brushing regimens is necessary. For 3 groups, the required effective sample size is 207 (69 x 3 groups), which taking into account missing and non-usable outcome data results in a proposed total sample size of 345 subjects (i.e. 207 / 0.60). For specific aim #2, it is difficult to estimate the expected proportion of HAs to occur in the respective treatment arms, particularly given the recent change in Centers for Disease Control and Prevention (CDC) National Healthcare Safety Network (NHSN) surveillance definitions for ventilator associated complications, including VAP. If the proportion of subjects who experience HAI within one of the treatment groups ( $n=69$ ) is 0.05, the corresponding 95% confidence interval would be 0.01 to 0.13, indicating reasonable precision.

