## IX. RESEARCH DESIGN AND METHODS

### Design

We will use a prospective, randomized, experimental design to accomplish the specific aims. Subjects (n=345) will be randomly assigned within 36 hours of intubation to one of three intervention groups which differ in frequency of tooth brushing (once, twice, or three times daily). The intervention, a standardized tooth brushing protocol developed and tested in the previous project, will be delivered by study personnel. Subjects will continue to receive scheduled interventions for the first 7 days of intubation, or until extubated if extubation occurs within 7 days; for subjects extubated within the intervention period, data collection will continue on days 1, 3, and 5 post-extubation. Dental plaque assessment, GCF for IL-1 $\beta$  determination, and data regarding HAIs and clinical status (for example, severity of illness) will be collected daily by study personnel who are blinded to group assignment.

All subjects will receive standard clinical care for mechanically ventilated patients, as per clinical guidelines and clinical agency guidelines. Standard clinical care includes all components of the IHI ventilator care bundle, including daily CHX. All subjects will receive oral comfort care by clinical providers at the provider's discretion. We will monitor reported compliance with the ventilator care bundle, and record characteristics and frequency of oral comfort care provided in order to assure that groups do not differ in usual clinical care.

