## Key Variables and Measurement

In this final phase of our investigation of oral care in mechanically ventilated adults, our goal is to determine optimal tooth brushing frequency. Taken as a whole, the work conducted in R01 NR007652 (the proposed project combined with the results of the previous and current projects) results in clear, complete, evidence-based guidance for nurses providing oral care to mechanically ventilated adults.

The primary aims of the proposed project are: 1) Evaluate the clinical equivalence (non-inferiority) of three tooth brushing frequencies on oral health (dental plaque and mucosal inflammation) in critically ill adults receiving mechanical ventilation; and 2) Quantify and compare the safety of three tooth brushing frequencies on serious adverse outcomes, including ventilator associated complications and clinically relevant HAIs (including VAP, bacteremia, and sepsis). A secondary aim is to investigate patient factors that influence tooth brushing frequency benefit and risk in critically ill adults.

We will accomplish these objectives using a prospective, randomized, experimental design. Subjects (n=345) will be randomly assigned within 36 hours of intubation to one of three intervention groups which differ in frequency of tooth brushing (once, twice, or three times daily). The intervention, a standardized tooth brushing protocol developed and tested in the previous project, will be delivered by study personnel for 7 days, or until extubated (if extubation occurs within the first 7 days). Key variables and their measurement intervals are presented in Table 1, and will be described more fully in the Research Design section.

Table 1: Key variables

Concept	Variable	Measurement interval
Oral Health (Specific Aim 1)	Dental Plaque: UM-OHI, augmented with DPIA	Daily for 7 days while intubated, days 1,3,5 post-extubation*
	Gingival inflammation: GCF IL-1 $\beta$	Daily for 7 days while intubated, days 1,3,5 post-extubation*
Serious outcomes (Specific Aim 2)	Systemic Inflammatory Response Syndrome criteria	Daily for 7 days while intubated, days 1,3,5 post-extubation*
	HAI: positive epidemiologic surveillance report for VAE (including VAP), bacteremia, sepsis	Daily for 7 days while intubated, days 1,3,5 post-extubation*
	Length of stay (ICU and hospital)	Calculated at hospital discharge
	Length of intubation	Calculated at time of extubation
Patient factors (Specific Aim 3)	Demographics (age, gender, smoking status)	On study admission

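### The primary ANCOVA adjusts for the day of each subject's own maximum plaque change, a post-randomisation variable selected by the outcome, and no non-inferiority analysis without it is planned

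*Combined protocol and SAP*

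**What the plan says.** Section XI, Specific Aim 1, takes as primary outcome "the maximum difference in dental plaque since baseline assessment at the time of intubation". The reason given is "Recognizing variable length of hospital stay and intubation". The once-daily and three-times-daily arms are compared by ANCOVA, and "timing of the assessment will be included as a covariate along with baseline dental plaque score". On the day of the maximum, the plan says "we would expect balanced distribution of the specific post-admission day in which this maximum difference is achieved between the 3 treatment arms". It offers no data for this, no check, and no rule if the arms differ.

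Once daily is non-inferior if the upper 95% confidence limit of the effect size is below 0.50. In Table 2 that result leads straight to the once-daily recommendation, with the rationale "1 time/day non-inferior and safe" and number needed to harm marked not applicable.

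The only other plaque model is the Aim 3 mixed model. It is exploratory and enters "random group assignment as a 3-level ordinal predictor variable", so it does not give the 1-versus-3 contrast that Table 2 needs.

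On follow-up, the Design section says "Subjects will continue to receive scheduled interventions for the first 7 days of intubation, or until extubated if extubation occurs within 7 days". It adds data collection on days 1, 3 and 5 after extubation for subjects extubated within that period, and Table 1 lists plaque among those measures. Table 1 also makes length of intubation an Aim 2 outcome ("Calculated at time of extubation").

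**The concern.** A covariate measured before randomisation sharpens the comparison without changing what is estimated. The day of the maximum is different. It arises after randomisation, and the same daily plaque scores that supply the outcome also select it. If more frequent brushing makes plaque fall faster, or keep falling for longer, the day shifts, and conditioning on it removes or adds part of the effect that Aim 1 asks about. If the plan's expectation of balance is right, the term removes no bias from this source and only reduces residual variance.

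At stake is the single contrast that decides the 1-versus-3 rows of Table 2. When it reads supported, no later step would catch an error, because the harm measure is then not consulted.

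Two gaps add to this. The plan does not say whether the maximum is the largest fall, rise or absolute change, and the day depends on that choice. It also does not say whether post-extubation scores count.

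**Working it through.** **1. The plan's own figure.** For margin 0.50 SD, true difference 0, one-sided alpha 0.10 and power 95%: n = 2(1.2816 + 1.6449)² / 0.50² = 68.5, so 69 per group. Then 3 × 69 = 207 and 207 / 0.60 = 345. All three agree with the Statistical Power section. No covariate adjustment enters, so changing the ANCOVA terms leaves them as they are.

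**2. Why the term can shift the estimate.** By least squares,

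adjusted difference = baseline-adjusted difference − b × Δ,

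where b is the slope of outcome on day of maximum and Δ is the baseline-adjusted arm difference in mean day. The shift is zero if Δ = 0 or b = 0. In one large simulated case (200,000 per arm), Δ = −0.16 days and b = −0.207 moved the estimate from 0.409 to 0.372 SD.

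**3. Size with equal observation time.** All inputs are assumed: 69 per arm, intubated days only, 2 to 7 observed days (uniform), extubation unrelated to plaque, baseline SD 2.0, daily error SD 1, no floor or ceiling, 6,000 trials per scenario. Background trends were −0.22, 0 and +0.15 points per day. The first is (7.3 − 6.0)/6 from preliminary study 4, which reports only lower bounds (above 73% and above 60%). The effect was set to about 0.50 residual SD in the arm-plus-baseline model. False non-inferiority means an upper 95% limit below 0.50, nominally 2.5%. Results are for a signed maximum.

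| Effect of frequency | Difference, with/without term | False non-inferiority, without → with |
|---|---|---|
| Accrues over days | 0.83 to 1.06 | 1.9–2.7% → 1.4–4.8% |
| Level shift | 1.00 in all six cases | 2.1–2.7% → 1.6–2.6% |
| Slower approach to the same plateau (largest fall) | 1.04 to 1.13 | 2.2–2.5% → 0.1–1.6% |

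The lowest ratio is 0.656 → 0.544 points. With residual SD about 0.656/0.50 = 1.31, that is 0.112/1.31 = 0.09 SD. A second simulation with other trajectories moved the estimate by 0.04 SD or less, in both directions. With an absolute maximum the ratio was 0.74 to 1.00 and sensitive to coding.

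**4. Unequal observation time, a separate mechanism.** A maximum over more days is more extreme. With no brushing effect, mean observed days 4.0 (once) and 5.0 (three times), and largest fall, the spurious difference in plaque points was:

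| Background per day | Arm + baseline | Plus day of maximum | Plus days observed |
|---|---|---|---|
| −0.22 | 0.290 | 0.121 | 0.000 |
| 0 | 0.152 | 0.112 | 0.000 |
| +0.15 | 0.092 | 0.091 | 0.001 |

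The timing term removes (0.290 − 0.121)/0.290 = 58%, (0.152 − 0.112)/0.152 = 26% and (0.092 − 0.091)/0.092 = 1%. A repeated-measures model, run for the first two backgrounds, gave 0.003 and −0.012 (Monte Carlo SE 0.007).

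With the effect at the margin and once daily observed a day longer, false non-inferiority was 12.4–43.2% without the timing term and 1.4–15.0% with it. With three times daily observed longer, both were below 2%. At 69 per group and SD of days 1.71, SE = 1.71 × √(2/69) = 0.29, so a one-day gap is 1/0.29 = 3.4 SE. It would need a real effect of arm on intubation time.

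**The case against.** The strongest reply is that the timing term does useful work. The plan chose this outcome because stay and intubation vary, and the term partly offsets unequal observation. In all five cases run at the margin with once daily observed a day longer, dropping the term did worse: 35.1 against 12.2%, 18.1 against 15.0%, 27.4 against 6.1%, 12.4 against 8.4%, and 43.2 against 1.4%. This stands. A reader might infer that deleting the term repairs the analysis; it does not.

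Adjusting for days observed did better. In a similar simulation (4,000 trials, largest fall, gaps of 0 to 1 day) it kept false non-inferiority at 2.8% or less in all 36 cells. But days observed is also post-randomisation, and the result assumes extubation unrelated to plaque, so it suits a sensitivity analysis only.

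The effect of the term itself is small. The worst figure with equal observation, 4.8%, is below the 0.10 used for sample size, although the decision rule as written is a 95% interval. The assumed scale is also strained: the score is bounded at 0 to 10, and with mean 7.3 and SD 2.0 about 9% of baselines would exceed 10. Both remarks stand.

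A reader might also infer that plaque assessment ends at extubation. The Design section and Table 1 say otherwise for subjects extubated within 7 days. The figures above count intubated days only, which is an assumption.

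**Conclusion.** The concern holds as a weakness in the estimand and in robustness. The decisive contrast is conditioned on a variable that the outcome itself selects, and no non-inferiority analysis without it is planned. With equal observation time the shift is modest and can go either way: ratio about 0.83 to 1.13, and false non-inferiority from about 2.5% to at most about 5%. It is nil for a level shift with a signed maximum.

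A reader might infer that the term favours once daily or could reverse the conclusion. The documents do not support that. They give no plaque SD, no between-arm trajectory and no arm difference in the day. Large errors require strong assumed inputs: a within-arm correlation of 0.6 between day and outcome, with a day imbalance of 0.75 SD, shifts the estimate by 0.6 × 0.75 = 0.45 SD, and nothing in the plan points to such values.

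Unequal observation time is the larger risk, but a separate one that neither version of the ANCOVA controls. The change is worth making and confidence is medium, because every magnitude rests on assumed inputs.

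**What to change.** In section XI, Specific Aim 1:

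1. Make the 1-versus-3 ANCOVA with arm and baseline plaque only the primary model. Keep the timing-adjusted model as a sensitivity analysis.
2. Report day of maximum and days observed by arm. Require two further analyses of the same contrast: an ANCOVA adjusted for days observed (sensitivity only), and a repeated-measures model of daily plaque with arm as a factor, day, arm-by-day and baseline, averaged over prespecified days.
3. Express all of them against the 0.50 margin using one common SD, the residual SD of the baseline-only ANCOVA. State in advance that if they disagree with the primary result, the Table 2 conclusion is reported as not robust.
4. Fix one signed direction for the maximum before unblinding, and state whether post-extubation scores count.

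The cost is a few sentences and two added models, with no new data and the sample size unchanged at 69/207/345. Without the timing term the standard error is about 0% to 6% larger where arm does not affect timing, or up to 10% if subjects differ in slope (assumed SD 0.2 per day). The primary model also loses its partial offset for unequal observation, which is why step 2 is required.
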